3. INTRODUCTION

Daprodustat (GSK1278863) is a small molecule, oral inhibitor of the hypoxia-inducible factor (HIF) prolyl-4-hydroxylase (PHD) enzymes which may present several important advantages over recombinant, human erythropoietin (rhEPO). It is an oral medication and does not require cold-chain storage as do some rhEPOs, thus increasing ease of use for patients. Moreover, data indicate that, similar to other HIF-PHD inhibitors, daprodustat can effectively raise hemoglobin (Hgb) concentrations with lower erythropoietin (EPO) levels than those observed after administration of rhEPOs (Besarab, 2015; Holdstock, 2016). Because of the increased cardiovascular (CV) risk associated with raising Hgb concentrations through large increases in EPO levels (Pfeffer, 2009), daprodustat has the potential to treat patients with less CV risk than rhEPOs. Additional benefits include the potential to treat anemia without causing rhEPO-induced hypertension, to improve iron availability for erythropoiesis, and the potential to successfully treat rhEPO hypo-responders (Holdstock, 2016).

3.1. Study Rationale

Sufficient iron availability is critical for normal erythropoiesis and all rhEPO labels carry guidance with regard to iron availability. It is anticipated that the majority of patients with chronic kidney disease (CKD) will require supplemental iron during the course of rhEPO therapy. However, poor compliance is seen with oral iron therapy due to gastrointestinal intolerance, while intravenous (IV) iron has an increased risk of infection and/or iron overload as well as an increased risk of anaphalaxis and congestive heart failure. Excess accumulation of iron in tissues with IV iron is clearly associated with increased morbidity and mortality with organ dysfunction primarily seen in the liver, heart, pancreas, joints and endocrine organs. Further, most of the morbidity and mortality due to iron overload disorders is the result of iron accumulation in the heart (Macdougall, 2016). Finally, administration of IV iron is associated with additional costs related to in-hospital administration and the need for patient monitoring.

Several proteins involved in iron absorption/metabolism are known to be HIF target genes. In this regard, daprodustat is equipotent against 3 human PHD enzymes (PHD1, PHD2 & PHD3) thereby stabilizing both HIF1 α and HIF2 α . Increased iron absorption correlates with increased expression in enterocytes and proerythroblasts of divalent metal-iron transporter 1 (DMT1), duodenal cytochrome b561 (DcytB) and ferroportin (FPN) mRNA. HIF-2 α is reported to up-regulate the expression of these genes by direct binding to consensus hypoxia response elements (HRE) (Koury, 2015). Thus, there is the potential that daprodustat administration, by virtue of increasing HIF levels, can increase oral iron absorption and incorporation into Hgb. Therefore, the purpose of this study is to compare the effect of daprodustat to rhEPO (i.e., epoetin alfa or darbepoetin alfa) on non-heme oral iron absorption using stable isotopic iron (⁵⁷Fe & ⁵⁸Fe) by measuring incorporation of iron in erythrocytes. The coordination of erythropoietin synthesis with iron metabolism by HIF is shown in Figure 1.

3.3.2. Benefit Assessment

In clinical trials of up to 24 weeks in duration, in participants with anemia associated with CKD, daprodustat has been shown to increase Hgb to target range. Data from prior studies with daprodustat suggest that the increases in Hgb are achieved with EPO levels lower than those observed with rhEPO (Holdstock, 2016).

3.3.3. Overall Benefit:Risk Conclusion

Daprodustat demonstrates a positive benefit vs. risk balance based on the evidence as follows. In clinical trials up to 24 weeks in duration, daprodustat maintained Hgb to target range in participants with anemia associated with CKD (both nondialysis dependent (ND) and hemodialysis dependent (HD)) with a safety profile consistent with the patient population.

This protocol employs precautions to mitigate known and potential risks to enrolled participants (See Appendix 3). Given these precautions, as well as the potential benefit that daprodustat holds for the treatment of anemia associated with CKD compared to the current standard, the overall benefit:risk balance is considered to be positive.

4. OBJECTIVES AND ENDPOINTS

Objectives	Endpoints
Primary	

 Compare the efficacy of daprodustat to rhEPO (i.e., epoetin alfa or darbepoetin alfa) on iron absorption 	
 Difference in fractional oral iron absorption (%) between daprodustat and rhEPO
Secondary	

 Characterize the effect of daprodustat or rhEPO on markers of iron status 	
 Change from baseline (Day 1) at 14 and 28 days following treatment with daprodustat or rhEPO in serum iron, transferrin, transferrin saturation, soluble transferrin receptor, ferritin, hepcidin and erythroferrone

 Characterize the effect of daprodustat or rhEPO on indices of erythropoiesis 	
 Change from baseline (Day 1) at 14 and 28 days following treatment with daprodustat or rhEPO in Hgb, hematocrit, red blood cell number, mean corpuscular volume, reticulocyte Hgb and reticulocyte number
Safety	

 Assess safety and tolerability 	
 Incidence and severity of adverse events and serious adverse events Reasons for discontinuation of study medication Vital signs assessments

5. STUDY DESIGN

[figure not shown]
5.1. Overall Design

This study will be a randomized, repeat dose, open label, two period cross-over study in adult, male and female participants with anemia associated with chronic kidney disease who are not on dialysis currently treated with stable doses ($\leq 50\%$ change in 4-weekly dose) for at least 8 weeks prior to and including the screening period, of rhEPO (i.e., epoetin alfa or darbepoetin alfa).

Sufficient participants will be enrolled such that at least 12 participants comprise the Evaluable Population (See Section 10.3.1.3).

The study design is outlined in Figure 2.

Figure 2 Study Design

- There will be a 4-week screening period in order to confirm that participants have stable Hgb levels and to assess entry criteria
- A 28-day Treatment Period 1 for incorporation of iron into erythrocytes while on randomized study treatment
- A 28-day Treatment Period 2 for a second incorporation of iron into erythrocytes while on randomized study treatment
- A follow-up visit 14 ± 3 days after completing treatment.

Participants will be randomly assigned either to remain on their current therapy (either epoetin alfa or darbepoetin alfa) or be switched to daprodustat for Treatment Period 1. For assessment of incorporation of iron into erythrocytes, enrolled participants will be administered ferrous sulfate containing a stable isotope of iron (^{57}Fe or ^{58}Fe) orally in a randomized fashion following 2 weeks of administration of randomized study treatment. Thus, there are 4 possible treatment sequences as shown in Table 1. Two weeks following oral iron administration a blood sample will be taken in order to assess the incorporation of the iron isotope into red blood cells by thermal ionization mass

spectrometry (TIMS) using published methods (IAEA Human Health Series No. 21, 2012).

At Day 29 participants will be crossed over to the study treatment they did not receive in Treatment Period 1, i.e., for participants that remained on their current therapy they would be switched to daprodustat, while subjects that had been administered daprodustat would be switched back to their previous therapy at the dose prior to randomization. At 2 weeks following initiation of dosing, participants will again be administered ferrous sulfate containing the stable iron isotope not administered following the assessment in Treatment Period 1 orally. Two weeks following oral iron administration a blood sample will again be taken in order to assess the incorporation of the iron isotope into red blood cells by TIMS.

Participants will attend a follow-up visit 14 ± 3 days following the final blood sample for assessment of red blood cell iron.

Table 1 Possible Treatment Sequences

	Sequence A N=3	Sequence B N=3	Sequence C N=3	Sequence D N=3
Treatment Period 1	rhEPO ⁵⁷ Fe	rhEPO ⁵⁸ Fe	Daprodustat ⁵⁷ Fe	Daprodustat ⁵⁸ Fe
Treatment Period 2	Daprodustat ⁵⁸ Fe	Daprodustat ⁵⁷ Fe	rhEPO ⁵⁸ Fe	rhEPO ⁵⁷ Fe

5.2. Number of Participants

Sufficient participants will be enrolled such that at least 12 participants comprise the Evaluable Population (See Section 10.3.1.3).

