7.3. Method of Treatment Assignment

All participants will be centrally randomized using an Interactive Voice/Web Response System (IVRS/IWRS). Before the study is initiated, the telephone number and call-in directions for the IVRS and/or the log in information & directions for the IWRS will be provided to each site.

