10.2. Sample Size Determination

Sufficient participants will be enrolled such that at least 12 participants comprise the Evaluable Population (See Section 10.3.1.3).

A sample size of 12 participants provides 90% power to detect a paired mean difference of 11% between the two treatment groups under an assumed between-participant standard deviation (SD) of 10.7%. Note this is a conservative estimate of the SD of the paired differences as it is based on a parallel design study (Young, 2009).

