1.1. Objectives, Estimands and Endpoints

Since the primary endpoint analyses are based on the Evaluable Population, subjects with intercurrent events who discontinue treatment in either period will be excluded from the primary analysis. Missing data post withdrawal will not be imputed.

Objectives	Endpoints
Primary	

 Compare the efficacy of daprodustat to rhEPO (i.e., epoetin alfa or darbepoetin alfa) on iron absorption 	
 Difference in fractional oral iron absorption (%) between daprodustat and rhEPO
Secondary	

 Characterize the effect of daprodustat or rhEPO on markers of iron status Characterize the effect of daprodustat or rhEPO on indices of erythropoiesis 	
 Change from baseline (Day 1) at 14 and 28 days following treatment with daprodustat or rhEPO in serum iron, transferrin, transferrin saturation, soluble transferrin receptor, ferritin, hepcidin and erythroferrone Change from baseline (Day 1) at 14 and 28 days following treatment with daprodustat or rhEPO in Hgb, hematocrit, red blood cell number, mean corpuscular volume, reticulocyte Hgb and reticulocyte number

Objectives	Endpoints
Safety	

 • Assess safety and tolerability 	
 • Incidence and severity of adverse events and serious adverse events • Reasons for discontinuation of study medication 
Vital signs assessments

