4.2.2. Main analytical approach

Endpoint / Variables

 Fractional oral iron absorption (%)
Model Specification

 To compare daprodustat to rhEPO on fractional iron absorption, a mixed effects model will be fitted Terms fitted in the mixed effect model will include:

Endpoint / Variables

 • Fixed effect: treatment, period, and iron isotope • Random effect: participant • The Kenward and Roger method for approximating the denominator degrees of freedom and correcting for bias in the estimated variance-covariance of the fixed effects will be used. • Using PROC MIXED in SAS, the covariance for the random participant effect (G matrix) will be fit using an unstructured covariance structure by specifying ‘type=UN’ on the RANDOM line. 
 • In the event that this model fails to converge, alternative covariance structures may be considered such as Variance Components or Compound Symmetry. • Akaike’s Information Criteria (AIC) will be used to assist with the selection of covariance structure.
Model Checking & Diagnostics

 • For the Mixed Model, model assumptions will be checked, and appropriate adjustments may be applied based on the data. • Distributional assumptions underlying the model used for analysis will be examined by obtaining a normal probability plot of the residuals and a plot of the residuals versus the fitted values (i.e. checking the normality assumption and constant variance assumption of the model respectively) to gain confidence that the model assumptions are reasonable. • If there are any departures from the distributional assumptions, alternative transformations, such as data squared or square root of data, will be explored. • Non-parametric analyses will be conducted if the normality assumption does not hold.
Model Results Presentation

Fractional oral iron absorption will be summarized using n, mean, SD, median, minimum, and maximum.
 
Point estimates, corresponding 95% confidence intervals, and two-sided p-values will be constructed for the comparison of efficacy of daprodustat to rhEPO.

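### The enrolment rule counts 12 evaluable participants overall but does not hold 3 per sequence, and the stated 90% power is slightly high for the planned model (88.5% at best with 12)

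*Protocol*

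**What the plan says.** The size target is worded the same way in Protocol 5.1, 5.2 and 10.2 and in SAP section 5: "Sufficient participants will be enrolled such that at least 12 participants comprise the Evaluable Population". It is a floor on the total.

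Table 1 in Protocol 5.1, repeated in SAP 1.2, shows N=3 for each of sequences A to D. These cross treatment order with isotope order.

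Protocol 7.3 says that randomisation is central through an IVRS/IWRS. No block size, per-sequence target or within-sequence replacement rule is given.

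Protocol 10.3.1.3 requires the iron absorption assessment in both periods for a participant to be evaluable. SAP 1.1 adds that "subjects with intercurrent events who discontinue treatment in either period will be excluded from the primary analysis". Protocol 8.2.1 lists many reasons for mandatory withdrawal after randomisation.

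The power statement in Protocol 10.2 is "A sample size of 12 participants provides 90% power to detect a paired mean difference of 11% between the two treatment groups". The SD behind it is 10.7%. The primary model in SAP 4.2.2 has "Fixed effect: treatment, period, and iron isotope", with a random participant effect.

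**The concern.** With 3 in each sequence, treatment is orthogonal to both period and isotope, so adjusting for them costs only two degrees of freedom. Participants are randomised before anyone knows whether they will be evaluable, and losses are foreseeable. A rule that looks only at the total can be met by an unequal split. The model then separates treatment from period and isotope using correlated terms, and the confidence interval for the primary difference widens. In a trial of about 12 people, one or two losses from the wrong sequences can do this. The stated power allows neither for the two extra model terms nor for any imbalance.

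**Working it through.** **Inputs from the documents.** n = 12 evaluable; difference 11; SD of paired differences 10.7 (Protocol 10.2); two-sided test (SAP 4.2.2), with alpha 0.05 inferred from the 95% interval; model terms from SAP 4.2.2; sequences from Table 1.

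**Assumed, because the documents give no figure.** Withdrawal of 10%, 20% or 30%, equal across sequences; randomised blocks of 4; enrolment ending at exactly 12 evaluable.

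**Step 1: the plan's own figure.** Paired t-test:
- SE = 10.7/√12 = 3.089; noncentrality = 11/3.089 = 3.56; df = 11.
- Power from the noncentral t = 89.9%. This matches the stated 90%.

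**Step 2: the SAP model.** Every evaluable participant has both treatments, both periods and both isotopes. The treatment effect is therefore the intercept when within-participant differences (daprodustat minus rhEPO) are regressed on period order (+1 for A and B, −1 for C and D) and isotope order (+1 for A and D, −1 for B and C). Residual df = 12 − 3 = 9, and the variance is SD² × [(X′X)⁻¹]₁₁.

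At 3/3/3/3 that element is 1/12, so the SE is still 3.089. Only the df change, and power is **88.5%**. The loss of 1.4 points (89.9 − 88.5) is present with no withdrawals at all.

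**Step 3: particular splits of 12 (in the order A/B/C/D).**

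| Split | Variance relative to 3/3/3/3 | Power |
|---|---|---|
| 3/3/3/3 | 1.000 | 88.5% |
| 4/2/4/2 | 1.000 | 88.5% |
| 4/3/3/2 | 1.029 | 87.7% |
| 4/4/2/2 | 1.125 | 84.7% |
| 5/4/2/1 | 1.346 | 78.0% |

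Example: for 4/4/2/2 the period column sums to 8 − 4 = 4 and the isotope column to 6 − 6 = 0. The variance element is 12/(144 − 16) = 0.09375, and 0.09375 × 12 = 1.125. For 4/2/4/2 both columns sum to zero, so nothing is lost. A surplus shared equally by A and C, or by B and D, is free.

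**Step 4: simulated enrolment to exactly 12 evaluable.** At least 20,000 trials per scenario:

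| Assumed equal withdrawal | Exact 3/3/3/3 | Mean power |
|---|---|---|
| 10% | 42% | 87.6% |
| 20% | 20% | 87.0% |
| 30% | 12% | about 86.3% |

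At 30%, one trial in ten has 82.6% or less. Power below 80% occurs in about 1.4% of trials at 20% withdrawal and about 4% at 30%. If withdrawal were 20% in A and B but 45% in C and D, mean power would be about 84.5%, and one trial in ten would have 78.0% or less.

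**Step 5: participants randomised if replacements go to short sequences.** Under equal withdrawal the expected number is the same under either rule: 12/0.8 = 15.0 at 20% and 12/0.7 = 17.1 at 30%. In the 20%/45% case, filling each sequence needs 6/0.8 + 6/0.55 = 18.4 on average, against about 17.8 when only the total counts. That is fewer than one extra.

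**The case against.** A reader might infer that enrolment stops at 12, that withdrawals are what push power below 90%, or that imbalance biases the treatment effect. The documents support none of these.

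- **The target is a floor.** Participants in progress when the twelfth becomes evaluable could take the total higher. Thirteen split 4/3/3/3 give 91.2%, and 14 split 4/4/3/3 give 93.3%. This stands, but nothing requires more than 12, and 12 is the number on which the power is justified.
- **The first 1.4 points come from degrees of freedom.** Holding 3 per sequence does not recover them. This stands.
- **Imbalance is usually cheap.** With blocking and equal withdrawal it costs about 1 to 2 points on average, and some splits cost nothing. This stands.
- **There is no bias from imbalance itself.** The model adjusts for period and isotope, so only precision suffers. This stands.
- **The SD matters more.** At a difference of 11, Protocol Table 5 runs from above 99% to 70% across its SDs, and the protocol calls 10.7 conservative. True, but balance helps at any SD.
- **The withdrawal rates are assumed.** The nearest figure, in Protocol Appendix 3, is 34% of non-dialysis participants meeting Hgb stopping criteria in an earlier study at 10 to 100 mg. This study uses 1 to 4 mg with a switch meant to keep Hgb unchanged, so the figure does not transfer directly.
- **The IWRS specification may already control balance.** It is not among the documents, so the gap is shown only for the protocol and SAP text. Blocks of 4 are a favourable assumption: unrestricted randomisation would give mean power of about 81%.

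**Conclusion.** The point holds as a minor one. The enrolment rule does not protect the 3-per-sequence split, and the stated 90% belongs to a simpler analysis than the one planned. With exactly 12 evaluable participants, a difference of 11 and an SD of differences of 10.7, the SAP model has 88.5% power at best. It averages roughly 86% to 88% at equal withdrawal of 10% to 30% with blocks of 4. Severe imbalance, with power in the 70s, is possible but uncommon unless withdrawal differs by sequence or randomisation is unrestricted. The consequence is a somewhat wider confidence interval. The validity of the primary comparison is not in question.

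**What to change.** 1. In Protocol 10.2 and SAP section 5, restate the power as about 88% for the SAP model with 12 evaluable participants at 3/3/3/3. If the split will not be held, give the lower figure together with the withdrawal rate and block size assumed.
2. In Protocol 5.1, 5.2 and 7.3, keep the target of 12 evaluable and add that each participant who does not become evaluable is replaced through the IWRS in a sequence still short of 3. The replacement is chosen at random among such sequences, and participants still in progress count as provisionally filling their place.

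**Cost.** A short text change, an IWRS setting and a slightly less favourable power figure. Late assignments become more predictable in an open-label trial, and fully so when only one sequence remains open. Central allocation does not remove that last case. The number randomised is unchanged on average if withdrawal is equal across sequences, and rises by less than one in the 20%/45% scenario.

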5.3. Participant and Study Completion

A participant is considered to have completed the study if he/she has completed all phases of the study including the follow-up visit.

The end of the study is defined as the date of the last visit of the last participant in the study.

5.4. Scientific Rationale for Study Design

This study will use a randomized, repeat dose, open label, two period cross over design in adult, ND, male and female participants with anemia associated with chronic kidney disease currently treated with stable rhEPO doses ($\leq 50\%$ change in 4-weekly dose) for at least 8 weeks prior to and including the screening period.

- This will be an open label study as oral iron absorption is an objective measure and unlikely to be influenced by the participant's knowledge of the treatment administered. Additionally, blinding of treatment would be difficult as rhEPO is

- administered by subcutaneous injection, while daprodustat is administered orally once daily as a tablet.
- Iron absorption will be assessed over a 2 week period commencing after 2 weeks of study treatment, a period of time when it is anticipated that any changes in oral absorption mediated by changes in expression of HIF-dependent DcytB and DMT1 will be apparent ([Shah, 2009](#)).
 - This study will use a cross over design, with oral iron absorption assessed in each participant following both rhEPO and daprodustat administration, in order for each participant to serve as their own control.
 - Participants will need to be currently treated with stable doses ($\leq 50\%$ change in 4-weekly dose) of rhEPO for at least 8 weeks prior to and including the screening period. Additionally, participants need to have stable Hgb levels for the 4 weeks of screening. Finally, participants will be switched from their current rhEPO to daprodustat using a switching algorithm that was designed to result in no change in Hgb levels. All of these aspects are intended to minimize any potential for a change in erythropoiesis during the course of the study in order to minimize any potential change in oral iron absorption due to a change in erythropoiesis ([Skikne, 2000](#)).
 - The planned population is participants currently on rhEPO for anemia associated with chronic kidney disease that are non-dialysis dependent. This population was chosen as those most likely to be administered oral iron therapy for the treatment of anemia. Additionally, as oral iron is inferior to IV iron likely due to elevated levels of hepcidin and pro-inflammatory cytokines that restrict intestinal iron absorption, this is the population most likely to benefit from an increase in oral iron absorption ([Macdougall, 2016](#)).
 - This study uses iron incorporation into erythrocytes in order to assess oral iron absorption. While it is appreciated that changes in erythrocyte iron content can be due to many factors, erythrocyte iron content is a well-recognized surrogate for iron absorption ([IAEA Human Health Series No. 21, 2012](#)). Additionally, fractional iron absorption as an endpoint allows for comparison to studies in non-anemic participants.
 - At present, three methodologies are primarily recognized for assessing fractional iron absorption: fecal recovery of the ingested isotope, plasma appearance of the ingested isotope and iron incorporation into erythrocytes following oral ingestion. Of the three, the most frequently used approach is iron incorporation into erythrocytes using single or multiple oral labels as it is more sensitive than either the fecal recovery or plasma appearance methods ([IAEA Human Health Series No. 21, 2012](#)). The majority (80%) of the iron that is absorbed is incorporated into red blood cells in Hgb, a process which occurs over 10 to 12 days. Once incorporated, the iron is stable for the lifespan of the red blood cell, a period of up to 120 days in non-anemic participants and approximately 70 days in individuals with chronic kidney disease.
 - Iron absorbed from the diet is obtained from animal-based sources, and is known as heme iron, while plant-based iron is non-heme iron. This study will assess the

absorption of non-heme iron as most of the understanding of iron absorption is related to non-heme iron which typically comprises the majority of dietary and supplemental iron.

- ND-CKD patients which have elevated levels of C-reactive protein (CRP) and hepcidin typically experience poor intestinal iron absorption ([Macdougall, 2014](#)). Therefore, hsCRP will be assessed at screening for eligibility in order to minimize the recruitment of participants with poor intestinal iron absorption due to inflammation.
- Finally, stable isotopic iron will be administered in the fasted state as the fraction of iron absorbed in the fasted state is typically much higher than that which occurs when a component of a mixed meal. A recent publication using this methodology in 18 healthy, adult female participants reported an average absorption \pm SD of $14.71 \pm 10.7\%$ in the fasted state compared to $3.63 \pm 6.5\%$ in the fed state ([Young, 2009](#)). In this regard, it is considered that a 30% change in oral iron absorption is clinically relevant.

